8.4.3 Time to MG-ADL response (≥ 2.0 points improvement from Baseline)

Time to MG-ADL response (in days) is defined as Date of First MG-ADL Response— Date of MG-ADL Baseline + 1.

Study participants who use rescue therapy prior to Day 43 or who are withdrawn from the treatment/study due to TEAEs before achieving first MG-ADL response will be censored at time of event. Study participants who never achieve a response by Day 43 will be censored at the date of their last MG-ADL assessment.

The number of study participants with 8, 12, 24, 32, 43 days to first MG-ADL response and number of censored study participants will be summarized descriptively.

Time to first MG-ADL response will be analyzed using a Cox Proportional Hazards model including fixed terms for treatment and stratification factors (MuSK+/- or AChR+/-). This model will be performed separately for study participants included in the interim analysis and for all study participants overall. Region may be added as an additional factor in the Cox Proportional Hazards model if it is significant in the primary analysis.

The Hazard Ratio (test/reference), 95% CI and p-values for each treatment comparison of interest will be presented for the Stage 1 (interim analysis), Stage 2 and overall (all data combined).

The log-hazard ratio, standard error estimates and (1-sided) p-values from the separate stage-wise Cox Proportional Hazards models for the relevant treatment group will be used to create overall p-values and repeated confidence intervals using the same methodology as the primary efficacy analysis.

The time to first MG-ADL response will be presented graphically using a Kaplan-Meier curve by treatment group, RLZ total. See details in [Section 9.3.2](#).

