	
• Change from Baseline to Day 43 (Visit 10) in the MG-Composite (MG-C) score• Change from Baseline to Day 43 (Visit 10) in quantitative myasthenia gravis (QMG) score• Change from Baseline to Day 43 (Visit 10) in the MG Symptoms patient-reported outcome (PRO) ‘Muscle Weakness Fatigability’ score• Change from Baseline to Day 43 (Visit 10) in the MG Symptoms PRO ‘Physical Fatigue’ score• Change from Baseline to Day 43 (Visit 10) in the MG Symptoms PRO ‘Bulbar Symptoms’ score 
The other efficacy endpoints are:
 
• Use of rescue therapy due to worsening (IVIg, PEX)• Time to first rescue therapy• Time to MG-ADL response (≥ 2.0 points improvement from Baseline)• Change from Baseline in QMG at each scheduled assessment during Treatment and Observation Periods• QMG responder (≥ 3.0 points improvement from Baseline) at each scheduled assessment during Treatment and Observation Periods• Change from Baseline in MG-C score at each scheduled assessment during Treatment and Observation Periods• MG-C responder (≥ 5.0 points improvement from Baseline) at each scheduled assessment during Treatment and Observation Periods• Change from Baseline in MG-ADL at each scheduled assessment during Treatment and Observation Periods
--	---

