Day (days) ^c	-28 to -1	1	3(±1)	8(±2)	15(±2)	22(±2)	24(±1)	29(±2)	36(±2)	43(±2)	57(±3)	71(±4)	85(±3)	99(±4)
Plasma complement levels (C3a and C5a) ⁿ		X							X					
MGFA classification	X	X								X				X
QMG scale	X	X		X	X	X		X	X	X		X		X
MG-C scale	X	X		X	X	X		X	X	X		X		X
MG-ADL	X	X		X	X	X		X	X	X	X	X	X	X
MG Symptoms PRO	X	X		X	X			X		X		X		X
PGI-S	X	X			X			X				X		X
PGI-C					X			X				X		X
EQ-5D-5L		X								X				
MGII ^o		X								X				
MG-QOL15r		X								X				
Study drug discontinuation criteria				X	X	X		X	X					
Study withdrawal criteria	X	X	X	X	X	X	X	X	X	X	X	X	X	X

AChR=acetylcholine receptor; ADA=anti-drug antibody; AE=adverse event; AESM=adverse events of special monitoring; BL=Baseline; C-SSRS=Columbia Suicide Severity Rating Scale; ECG=electrocardiogram; EQ-5D-5L=EuroQol-5D-5L; EOS=End of Study; EOT=End of Treatment; GI=gastrointestinal; HIV=human immunodeficiency virus; IgA=immunoglobulin A; IgE=immunoglobulin E; IgG=immunoglobulin G; IgM= immunoglobulin M; IGRA=interferon-gamma release assay; IMP=investigational medicinal product; INR=international normalized ratio; IRT=interactive response technology; MG=myasthenia gravis; MG-ADL=myasthenia gravis-Activities of Daily Living; MG-C=Myasthenia Gravis Composite; MGFA=Myasthenia Gravis Foundation of America; MGII=Myasthenia Gravis Impairment Index; MG-QOL15r=Myasthenia Gravis Quality of Life; MuSK=muscle-specific kinase; PEOT=premature end of treatment; PGI-C=Patient Global Impression of Change; PGI-S=Patient Global Impression of Severity; PK=pharmacokinetics; PTT=partial thromboplastin time; PRO=patient-reported outcome; QMG=Quantitative Myasthenia Gravis; TB=tuberculosis; V=Visit

^a This visit can be scheduled as a home visit, unless the study participant prefers to attend the site.

^b This visit will be a virtual visit, unless the study participant prefers to attend the site.

- ^c A visit window of ± 1 day is allowed for V3 and V7. A visit window of ± 2 day is allowed for all dosing visits. The visit window of ± 2 days is relative to the first dosing visit date. However, there should be a minimum interval of 5 days and maximum interval of 9 days as compared to the previous dose. A visit window of ± 3 days is allowed for V11 and V13. A visit window of ± 4 days is allowed for V12 and V14.
- ^d Refer to Section 1.4.
- ^e Only weight will be repeated at Baseline (V2).

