9.4.2 Analysis of secondary and other efficacy endpoints

All continuous secondary efficacy variables will be analyzed using the combination testing strategy and model defined for the primary analysis. The binary secondary efficacy variable of MG-ADL responder (≥ 2.0 points improvement from Baseline) at Day 43 (Visit 10) will be analyzed using logistic regression, including a term for Baseline MG-ADL score, treatment group, and a term for the stratification factor (categorized as AChR or MuSK).

In addition, all continuous secondary efficacy variables will be listed and summarized descriptively by treatment group and week. Descriptive statistics will be generated for the observed values and the change from Baseline. For the binary variable, frequency counts and percentages will be produced.

A sequential hierarchical test procedure will be applied to protect the overall significance level for the multiplicity of endpoints. The predefined order of formal hypotheses testing for the secondary endpoints will be performed in the following sequence:

- Change from Baseline to Day 43 (Visit 10) in MG-C score.
- Change from Baseline to Day 43 (Visit 10) in QMG score.
- Change from Baseline to Day 43 (Visit 10) in the MG Symptoms PRO ‘Muscle Weakness Fatigability’ score.
- Change from Baseline to Day 43 (Visit 10) in the MG Symptoms PRO ‘Physical Fatigue’ score.
- Change from Baseline to Day 43 (Visit 10) in the MG Symptoms PRO ‘Bulbar Symptoms’ score.

All other variables will be listed and summarized descriptively. Time to first MG-ADL response (defined as ≥ 2.0 point improvement from Baseline) will be analyzed using a Cox Proportional Hazards model including a fixed term for treatment, and a term for the stratification factor (categorized as AChR or MuSK). The statistical model will be applied to each stage and the results combined using in a similar fashion to the primary analysis. An overall study used to

calculate the Hazard Ratio (test/reference), 95% CI and p-values for each treatment comparison of interest will be presented. The time to first MG-ADL response will be presented graphically using a Kaplan-Meier curve. Study participants will be censored at time of initiation of rescue therapy or end of treatment.

Further exploratory analysis may be performed using adequate statistical methods; details will be provided in the SAP.

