8.2.2 Primary analysis of the primary efficacy endpoint

The primary analysis is based on the RS under the hypothetical & treatment policy strategy (see details in [Section 8.1](#)). Any missing MG-ADL scores (including missing data after the intercurrent events) will be handled based on maximum likelihood estimation method under MAR assumption.

A stage-wise MMRM with treatment group, Baseline MG-ADL score, region, stratification factor(s) including MuSK(+/-) and /or AChR(+/-), and treatment group by day (interaction term) as fixed factors and study participant as a random effect. The MMRM will include Days 8, 15, 22, 29, 36 and 43.

The model will utilize an unstructured covariance pattern for the repeated measures. If the model does not converge using the unstructured pattern, then an autoregressive covariance structure

will be used. The Kenward-Roger approximation will be used to estimate the denominator degrees of freedom.

For each stage, the least squares means (LSMs) of each treatment group, and the least squares mean differences (LSMDs) between each dose group and placebo will be reported for Day 43 (Visit 10), along with the corresponding 2-sided 97.5% CIs and p-values.

The study follows a 2-stage group sequential adaptive design using combination test (Lehmacher and Wassmer, 1999) based on the inverse-normal method of combining independent stagewise p-values (Hedges and Olkin, 1985)

The analysis takes into account that the study is a 2-stage group sequential adaptive design assuming equal weighting of each stage, with weights = $1/\sqrt{2}$:

- Stage 1 – Cohort up to the formal IA
- Stage 2 – Cohort post-IA

The following sequential test statistic will be used to test the global null hypothesis at the end of stage 2:

$$T = \sum_{i=1}^2 w_i \phi^{-1}(1 - p_i)$$

Where subscript $i = 1, 2$ represents the stage, p_i represents the appropriate multiplicity adjusted p-value at stage i (for example at stage 1, $p_1 = \min(2 * p_{\min}, 1)$ where p_{\min} is the minimum of the two nominal p-values), the weights $w_{ki} = 1/\sqrt{2}$ satisfy $\sum_{i=1}^2 w_{ki}^2 = 1$ and ϕ^{-1} is the inverse cumulative standard normal distribution function. The test statistic T and $z = \phi^{-1}(1 - p_i)$ have a standard normal distribution, (Lehmacher and Wassmer, 1999).

The combined p-value (2-sided) for the 2 stages, which tests the global null hypothesis, can be calculated by:

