8.4.2 Time to first rescue therapy

Time to first rescue therapy (in days) is defined as: Date of first rescue therapy use-- Date of first IMP + 1.

Time to first rescue therapy will be estimated and presented using the Kaplan-Meier product-limit method for each treatment. Study participants who do not take rescue therapy will be censored at the date of withdrawal/study completion. Where there are several AEs which led to drop out, consider the earliest starting AE.

The number of study participants with first rescue therapy and number of censored study participants up to 8, 12, 24, 32, 43, 57, 71, 85, 99 days will be summarized using descriptive statistics.

The median time to first rescue therapy, including the two-sided 95% CI, will be calculated for each treatment.

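### Time to first MG-ADL response: the summary days in SAP 8.4.3 do not match the MG-ADL visits, and the censoring rule has no cap at Visit 10, unlike Protocol 9.4.2

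*SAP*

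**What the plan says.** **Time scale.** SAP 8.4.3: "Time to MG-ADL response (in days) is defined as Date of First MG-ADL Response", minus the Baseline MG-ADL date, plus 1. These are actual dates, not nominal visit days.

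**Summary rows.** The same section asks for "The number of study participants with 8, 12, 24, 32, 43 days to first MG-ADL response", with the number censored. SAP 8.4.2, on time to first rescue, uses the same first five values and extends them: "number of censored study participants up to 8, 12, 24, 32, 43, 57, 71, 85, 99 days".

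**Assessment days.** SAP 8.2.2: "The MMRM will include Days 8, 15, 22, 29, 36 and 43". These are the MG-ADL visits of the Treatment Period in the Protocol 1.3 schedule. For Visits 4, 5, 6, 8 and 9, "A visit window of ± 2 day is allowed for all dosing visits". Visit 10 is not a dosing visit; its ±2 days stand in the header of the schedule. MG-ADL continues at Visits 11 to 14 (nominal Days 57, 71, 85 and 99), and the protocol lists as an endpoint "Change from Baseline in MG-ADL at each scheduled assessment during Treatment and Observation Periods".

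**Censoring.** SAP 8.4.3: "Study participants who never achieve a response by Day 43 will be censored at the date of their last MG-ADL assessment". Protocol 9.4.2: "Study participants will be censored at time of initiation of rescue therapy or end of treatment". SAP 3.9, which records departures from the protocol's analyses, does not mention this one.

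**The concern.** Three things do not fit together.

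- The row days are not the visit days, and the first and last rows cut through a visit window. The table then depends partly on which day within the window a visit took place.
- Day 43 is used on a time scale of actual dates without saying whether it is the calendar day or the name of Visit 10. Two programmers could reach different event counts.
- The censoring sentence has no upper limit. For someone who completes the study, the last MG-ADL assessment is Visit 14, eight weeks after the last visit at which a response is meant to count.

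Speed of onset is one of the reasons Protocol 4.3 gives for including the higher dose, so this table and curve will be read with interest. SAP 8.4.3 also produces hazard ratios, combined p-values, repeated confidence intervals and a Kaplan-Meier plot from these data.

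**Working it through.** **1. Can the row days be derived from the schedule?** No simple rule gives 8, 12, 24, 32, 43:

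| Candidate | Days |
|---|---|
| Nominal visit days | 8, 15, 22, 29, 36, 43 |
| Window ends (+2) | 10, 17, 24, 31, 38, 45 |
| Window starts (−2) | 6, 13, 20, 27, 34, 41 |
| Midpoints between visits | 11.5, 18.5, 25.5, 32.5, 39.5 |

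Only 8 and 43 are nominal MG-ADL days.

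**2. Where does each in-window assessment land?** Assign each day to the first row at or after it, taking the Baseline MG-ADL to be on Day 1:

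| Visit | Window | Row |
|---|---|---|
| 4 | 6–10 | Days 6–8 at 8; Days 9–10 at 12 |
| 5 | 13–17 | 24 |
| 6 | 20–24 | 24 |
| 8 | 27–31 | 32 |
| 9 | 34–38 | 43 |
| 10 | 41–45 | Days 41–43 at 43; Days 44–45 in no row |

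Late Visit 4 responses are deferred by one row. Visits 5 and 6 are merged, and Visit 9 shares the last row with the first three days of Visit 10. Late Visit 10 responses are in no row.

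**3. How large is the late share?** The documents give no distribution of visit days, so the following are assumptions. Late share = P(+1 day) + P(+2 days).

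- Uniform over ±2: 0.20 + 0.20 = 40%
- Half on the nominal day (0.10, 0.15, 0.50, 0.15, 0.10): 0.15 + 0.10 = 25%
- 70% on the nominal day (0.05, 0.10, 0.70, 0.10, 0.05): 0.10 + 0.05 = 15%

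For Visit 4 this share is deferred to the 12-day row. For Visit 10 it leaves the table.

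**4. What does the censoring rule do?** Visit 14 is Day 99 ± 4, so a completing non-responder is censored on Days 95–103. Under Protocol 9.4.2, with end of treatment at Visit 10, it would be Days 41–45. The nominal gap is 99 − 43 = 56 days.

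**5. Does this move the hazard ratio?** In 200 simulated two-arm trials (assumed: 67 per arm, 15% response per visit on placebo, 1.8 times that on active, uniform visit days):

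| Meaning of Day 43 | Censored at | Mean events | HR |
|---|---|---|---|
| Calendar day | Day 43 | 94.2 | 1.98 |
| Calendar day | about Day 99 | 94.2 | 1.98 |
| Visit 10 | own Visit 10 | 97.7 | 1.97 |
| Visit 10 | about Day 99 | 97.7 | 1.98 |

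HRs are exponentiated mean log hazard ratios. Under the calendar-day reading the two censoring rules give the same log hazard ratio (largest difference 9e-16), because no event follows Day 43. Under the visit reading the largest difference in a single trial was 0.14. The calendar-day reading costs 97.7 − 94.2 = 3.5 events on average.

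**The case against.** The case for leaving the text alone is substantial.

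- **A reader might infer that late Visit 4 responses are missed.** They are not. Visit 4 ends on Day 10 and the next row is 12. The wording of SAP 8.4.2 supports cumulative rows, so these responses are only deferred, and an 8-day row on an actual-day scale correctly shows responses within 8 days. The same wording argues against reading the rows as exact days.
- **A reader might infer that late Visit 10 responders are censored in the Cox model, contradicting SAP 8.3.1, which counts them as Day 43 responders.** That requires Day 43 to be the calendar day. The endpoint definitions pair Day 43 with Visit 10, SAP 3.2.1 analyses by scheduled visit, and SAP 3.2.2 ends the Treatment Period after the Day 43 assessments. The visit reading is the more natural one and removes the conflict. SAP 8.4.3 does not settle it, but the loss of events is not established.
- **The cap may be implied.** The rows in 8.4.3 stop at 43, while those in 8.4.2 run to 99. This suggests a Visit 10 horizon was intended. It is a fair inference, but the censoring sentence itself states no limit.
- **A first response at Visit 11 is a non-event under the protocol too.** True. The difference is that the literal SAP rule also shows that person as event-free to about Day 99.
- **Responder rates by visit are already in SAP 8.4.9.** They are, and they answer much of the onset question. They are proportions responding at each visit, however, not the cumulative proportion with a first response.
- **The hazard ratio barely moves, and this is an other efficacy endpoint outside the testing sequence of SAP 4.6.** Both points stand and limit the severity.

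**Conclusion.** The point holds in limited form. The row days do not match the MG-ADL schedule, and Visit 10 first responses on Days 44–45 are certain to be absent from the descriptive table if it uses actual days as defined: 15% to 40% of Visit 10 first responses under the assumed distributions. Their loss from the Cox and Kaplan-Meier analyses is conditional on the calendar-day reading, which the rest of the SAP does not favour.

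Taken literally, the censoring rule departs from Protocol 9.4.2 without an entry in SAP 3.9. It extends follow-up of completing non-responders by about 56 days, gives a flat off-drug Kaplan-Meier tail with inflated numbers at risk, and shows people who first respond at Visit 11 or later as event-free to about Day 99. A reader might infer a biased treatment comparison; the simulation does not support that (mean HR 1.97 against 1.98, or identical), within its assumed response rates and arm size. Severity is low.

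**What to change.** In SAP 8.4.3:

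1. Tabulate first response by scheduled visit (4, 5, 6, 8, 9, 10), or cumulatively at window-end Days 10, 17, 24, 31, 38 and 45. With those days every in-window assessment falls in its own visit's interval.
2. State that Day 43 means Visit 10 including its window.
3. Censor non-responders at their last MG-ADL assessment up to and including Visit 10, in line with Protocol 9.4.2, or list the departure in SAP 3.9.

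One caution on item 3. If the Kaplan-Meier curve stays on actual days, non-responders seen early in the Visit 10 window leave the risk set before later responders are counted, and the last step is too large. With a true 15% response at Visit 10 and uniform days (both assumed), the curve would show 1 − (1 − 0.15/5)(1 − 0.15/4)(1 − 0.15/3)(1 − 0.15/2)(1 − 0.15) = 30%. Coding time by scheduled visit, so that Visit 10 events and censorings share one time point with events first, avoids this.

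The cost is SAP wording, table shells and a small programming change. No new data are needed.

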4 STATISTICAL/ANALYTICAL ISSUES

4.1 Adjustments for covariates

The efficacy analyses will be adjusted for the following covariates:

- Baseline MG-ADL score,
- Region (North America, Europe, and Asia [excluding Japan], Japan),
- Stratification factors – MG-specific autoantibodies, including muscle specific kinase [MuSK(+/-)] and acetylcholine receptor [AChR(+/-)], both as binary variables.

In statistical modeling, the stratification factors MuSK(+/-) and AChR(+/-) will be based on the values from MG-specific autoantibody assessment at Baseline. In case Baseline MG-specific autoantibody result is missing (and not resolved after data queries), a post-Baseline measurement may be used. If this is not available, then the historical result will be used in the model; if the historical result is missing as well, the stratification factor from IWRS randomization file will be used to determine values used in the model (i.e., if the stratification is MuSK in IWRS, then

MuSK(+/-) will be imputed as positive, otherwise negative; similarly, if stratification factor is AChR in IWRS, then AChR(+/-) will be imputed as positive, otherwise negative).

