8.3.1 MG-ADL Responder Rate at Visit 10 (Day 43)

See [Section 8.2.1](#) for the derivation of MG-ADL total score.

Study participants will be classified as responders at Visit 10 if the value is at least a 2-point improvement (decrease) from Baseline at Visit 10 (Day 43).

Analysis will be based on the RS under the composite strategy (see details in [Section 8.1](#)). Any missing data scores (including missing data due to the intercurrent events) will also be imputed as non-responders. Note that this endpoint is not part of the formal secondary endpoint testing strategy.

The number and percentage of study participants who are MG-ADL responders at Day 43 will be presented by treatment group and RLZ total for each stage. The odds ratio of the responder rates at Day 43 will be estimated and tested between treatment groups (each rozanolixizumab dose vs placebo) for each stage separately using logistic regression model with factors of treatment group, Baseline MG-ADL score and stratification factors (MuSK+/- and AChR+/-). The odds ratio with associated 95% CI and p-value based on the Wald test will be presented. Region may be added as an additional factor in the logistic regression model if significant in the primary analysis.

The odds ratios, 95% CIs, and p-values from each stage will be combined using the same inverse normal method used in the primary efficacy endpoint.

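### The Cox model for time to MG-ADL response omits Baseline MG-ADL, leaves region optional and names no tie method, out of line with SAP 4.1; a minor, cost-free repair

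*SAP*

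**What the plan says.** SAP 4.1 sets a general rule: "The efficacy analyses will be adjusted for the following covariates". The list is Baseline MG-ADL, region and the two antibody factors (MuSK and AChR), with no exception stated.

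SAP 8.4.3 says that time to first MG-ADL response "will be analyzed using a Cox Proportional Hazards model including fixed terms for treatment and stratification factors", the factors being the antibody ones. It adds: "Region may be added as an additional factor in the Cox Proportional Hazards model if it is significant in the primary analysis". Protocol 9.4.2 gives the same core model, "including a fixed term for treatment, and a term for the stratification factor", also without Baseline MG-ADL.

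For the same 2-point response taken as a binary endpoint at Day 43, SAP 8.3.1 uses a "logistic regression model with factors of treatment group, Baseline MG-ADL score and stratification factors", and Protocol 9.4.2 likewise specifies a model "including a term for Baseline MG-ADL score, treatment group, and a term for the stratification factor".

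Event time in 8.4.3 runs from the Baseline assessment to the date on which response is first recorded. Neither document names a tie method, an interval-censored model or a discrete-time model. The descriptive summary is "The number of study participants with 8, 12, 24, 32, 43 days to first MG-ADL response", together with the number censored.

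**The concern.** The chance of a 2-point fall plausibly depends on where a participant starts. Entry allows an MG-ADL score of 3 (Protocol 5.1, criterion 5a), and from there response means reaching 1 or lower. The score is collected for everyone and enters the primary model and the logistic responder model, yet not this one. Two programmers working from 4.1 and from 8.4.3 could fit different models and each claim to follow the plan.

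Response can be observed only at visits, so many event times coincide or nearly coincide, and the estimate then depends partly on a tie option that the plan leaves open.

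Speed of onset has a role in this trial. Protocol 4.3 cites time to onset of symptom relief among the reasons for including the higher dose, and SAP 8.4 keeps this as the only other efficacy endpoint analysed by stage.

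**Working it through.** **Plan's own figure.** The plan gives no hazard ratio, event count or power for this endpoint, so there is nothing to reproduce directly. The nearest figure is Table 2-1 for the primary endpoint. Simulating that two-stage design gives power 0.949 and average N 190.3 in scenario 7, against the stated 0.943 and 189.9. This confirms the reading of the design but does not bear on the Cox model.

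**Inputs from the documents.** MG-ADL is assessed at Days 8, 15, 22, 29, 36 and 43, each ±2 days (Protocol 1.3). There are 30 per arm in Stage 1 and 30 to 50 in Stage 2 (SAP 2.4), so 60 per arm is the minimum for a retained dose. The default test level is two-sided 0.05 (SAP 3.1).

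**Assumptions not in the documents.** True conditional hazard ratio (HR) 2.0; placebo response by Day 43 of 40% or 60%; Baseline log-HR of 0, 0.3 or 0.6 per SD.

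**Anchor.** With placebo response p0, active response is p1 = 1 − (1 − p0)². Events are d = 60(p0 + p1), and power is Φ(ln 2 × √d / 2 − 1.96).
- p0 = 0.4: p1 = 0.64, d = 62.4, power 0.782 (simulated with exact times: 0.778).
- p0 = 0.6: p1 = 0.84, d = 86.4, power 0.896 (simulated: 0.905).

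**Effect of adding Baseline** (Efron ties, ±2-day windows, 1,000 runs per setting):

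| Placebo response | Log-HR per SD | HR without → with | Power without → with | Gain, points |
|---|---|---|---|---|
| 40% | 0 | not reported | 0.777 → 0.769 | −0.8 |
| 60% | 0 | 2.02 → 2.03 | 0.893 → 0.890 | −0.3 |
| 40% | 0.3 | 1.98 → 2.03 | 0.760 → 0.781 | 2.1 |
| 60% | 0.3 | 1.96 → 2.03 | 0.879 → 0.893 | 1.4 |
| 40% | 0.6 | 1.89 → 2.05 | 0.704 → 0.793 | 8.9 |
| 60% | 0.6 | 1.82 → 2.02 | 0.781 → 0.874 | 9.3 |

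A separate simulation (65 per arm, control hazard 0.03/day, responses seen only at the nominal days, two-sided 0.025, 1,500 runs) agrees under Efron. At Baseline HR 1.35 per SD (ln 1.35 = 0.30) power goes from 0.879 to 0.901, a gain of 2.2 points. At 1.65 (ln 1.65 = 0.50) it goes from 0.801 to 0.878, a gain of 7.7.

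**Effect of the tie method** (power without Baseline, same settings as the table above):

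| Placebo response | Log-HR per SD | Exact times | Strict grid: Efron / Breslow | ±2-day windows: Efron / Breslow |
|---|---|---|---|---|
| 40% | 0 | 0.778 | 0.780 / 0.746 | 0.777 / 0.763 |
| 60% | 0 | 0.905 | 0.899 / 0.855 | 0.893 / 0.878 |
| 40% | 0.3 | 0.770 | 0.769 / 0.720 | 0.760 / 0.748 |
| 60% | 0.3 | 0.875 | 0.869 / 0.822 | 0.879 / 0.844 |
| 40% | 0.6 | 0.701 | 0.707 / 0.653 | 0.704 / 0.688 |
| 60% | 0.6 | 0.782 | 0.781 / 0.704 | 0.781 / 0.758 |

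Efron stays within about 1 point of the exact-time analysis. Breslow costs 1.2 to 3.5 points relative to Efron with windows (above 3 in one setting), and 3.4 to 7.7 on a strict grid (above 7 in one setting).

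**Type I error.** With a true HR of 1, rejection was 0.030 to 0.052 in every setting.

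**Summary days.** The visit windows are Days 6–10, 13–17, 20–24, 27–31, 34–38 and 41–45. As cumulative cut-offs, Day 12 falls between Visits 4 and 5, Day 24 is the upper limit of Visit 6, and Day 32 falls between Visits 8 and 9. Day 8 splits the Visit 4 window and Day 43 splits the Visit 10 window.

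**Limits.** Monte Carlo standard error is about 1.3 points at 80% power, though compared analyses share data. The 60-per-arm Cox simulation is two-arm and pooled over stages, without dropout, rescue censoring or stage-wise combination.

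**The case against.** SAP 4.1 is a general list that the endpoint sections adapt. SAP 8.4.1 uses an unadjusted chi-squared test, 8.4.2 is Kaplan-Meier only, and region is conditional in 8.3.1 as well as 8.4.3. The logistic model is therefore not fully in line with 4.1 either. The SAP Cox model also follows Protocol 9.4.2 in leaving Baseline out, so SAP 3.9, which records departures from the protocol, had nothing to list. This stands to the extent that 4.1 cannot be read as a strict requirement for every endpoint. It does not explain why the two regression models for the same response treat Baseline differently.

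Omitting Baseline is also not bias in the usual sense. Hazard ratios are non-collapsible, so the unadjusted model targets a marginal hazard ratio and the adjusted one a conditional hazard ratio. The unadjusted estimate is attenuated only relative to the conditional value, and the test remains valid. This stands in full.

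A reader might infer that the analysis as written must understate the drug's effect and lose much power. In the 65-per-arm simulation, no Baseline with Breslow ties gives 0.775 against 0.901 for Baseline with Efron, and 0.665 against 0.878 with the stronger Baseline effect: losses of 12.6 and 21.3 points. The documents do not support that reading. Of those losses, 10.4 points (0.879 − 0.775) and 13.6 points (0.801 − 0.665) come from Breslow ties, which the SAP does not specify. They also come from a strict grid without visit windows and a placebo response of 1 − exp(−0.03 × 42) = 72%, which neither document gives.

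Nor is the whole set of summary days misplaced: three of the five respect the windows, and the table is descriptive only.

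**Conclusion.** The inconsistency is real: Baseline MG-ADL is missing from the Cox model in both documents, region is optional in 8.4.3 but not in 4.1, and no tie method is named. The loss is conditional on a prognostic strength that the documents do not give. At an assumed conditional HR of 2.0 with Efron ties it runs from none, through about 2 points, to about 8 to 9 points over the range tried. Visit grouping adds almost nothing under Efron and a small to moderate loss under Breslow.

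Severity is minor. This is an other efficacy endpoint (SAP 2.2.1.3), outside the gatekeeping procedure for the primary and five secondary endpoints (SAP 4.6), and no confirmatory conclusion rests on it.

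**What to change.** - In SAP 8.4.3, add Baseline MG-ADL to the Cox model. Record it in SAP 3.9, since Protocol 9.4.2 also lacks it.
- Reconcile region: either include it unconditionally in 8.4.3 or state the exception in 4.1. The same sentence in 8.3.1 should be settled at the same time.
- Name Efron or exact ties, or use a discrete-time complementary log-log model on the visit scale.
- Tabulate first response by scheduled visit (Visits 4, 5, 6, 8, 9 and 10) in place of the listed days.

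The cost is SAP wording and a few lines of code, with no new data. It should be settled before unblinding, so that the choice of covariates and tie method cannot be seen as results-driven.
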